## STUDY OVERSIGHT

Compliance to protocol and Data Integrity were maintained. Patient care data were stored and secured. Study recruitment criteria were reported to DSMB quarterly and IRB annually. Compliance measurements were documented as intake volumes, feeding durations, feeding positions, postprandial positions and symptom scores, growth metrics and nutritional status. Compliance to administration of omeprazole was confirmed using electronic medical records

(Epic, Epic Systems Corporation, Verona, WI, USA) and or parental validation. Trial protocol and important changes to methods after trial commencement are listed in **Supplement 1**.

## STATISTICAL METHODS

Based on our preliminary data, we had planned to enroll 100 patients (50 per group) to detect 27% or higher increase in proportion of success of study group compared to the conventional group with 80% power and overall one-sided  $\alpha$  level of 0.025. One interim futility analysis was planned at about 50% information prior to the final analysis at 100% information, corresponding to 50 and 100 evaluable patients, respectively. The boundary was determined using Lan-DeMets spending functions to simulate O'Brein-Fleming boundaries(34). Using the target proportion of success, the boundary at the futility analysis was  $p>0.297$ .

Seventy-six infants were randomly assigned till the end of funding for this study and were included in the analysis of demographics and clinical characteristics (**Fig 1, Table 1**) and primary outcome by intent-to-treat. If a patient dropped out before the end of study and no symptom score was evaluable, we treated the patient as a failure for the primary outcome by intention-to-treat. Secondary outcome analysis was performed for 72 subjects (**Fig 1**). Futility boundary was not reached at interim analysis of 50 patients ( $p=0.1 < 0.297$ ) and accrual was continued with DSMB approval. Summary statistics were calculated for patient demographics and clinical characteristics for final analysis. Success rate in achieving PO or reduction in the I-GERQ-R by 6-points was calculated with 95% confidence interval and compared using chi-square test between the conventional and study groups (primary outcomes) for the intention-to-treat and treat-as-treated analyses. Fisher's exact or chi-square test were used to compare other categorical secondary outcomes including feeding method and supplemental oxygen between the groups. Shapiro-Wilk test for normality was used for the continuous outcomes. Paired t-tests or Wilcoxon singed-rank

tests were used to assess changes in growth velocity and feeding therapy characteristics between time-1 and time-2. Two sample t-tests or Wilcoxon rank-sum tests were used to compare these continuous outcomes between conventional and study groups. Median (interquartile range [IQR]), mean (SD), or % was reported, unless stated otherwise.  $P$  values  $<0.05$  were considered statistically significant, and SAS version 9.4 (SAS, Inc, an IBM Company, Chicago, IL) was used.

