## **ABSTRACT**

**OBJECTIVE:** To test the hypothesis that a feeding-bundle concurrent with acid-suppression is superior to acid-suppression alone in improving gastroesophageal reflux disease (GERD) attributed-symptom scores and feeding outcomes in neonatal ICU infants.

**METHODS:** Infants (N=76) between 34-60 weeks' postmenstrual age with acid reflux index>3% were randomly allocated to study (acid suppressive therapy + feeding bundle) or conventional (acid suppressive therapy only) arms for 4 weeks. Feeding bundle included: total fluid volume <140 ml/kg/day, fed over 30 min in right lateral position, and supine postprandial position. Primary outcome was independent oral feeding and/or  $\geq 6$ -point decrease in symptom score (I-GERQ-R). Secondary outcomes included growth (weight, length, head circumference), length of hospital stay (LOHS, days), airway (oxygen at discharge), and developmental (Bayley scores) milestones.

**RESULTS:** Of 688 screened: 76 infants were randomized and used for the primary outcome as intent-to-treat, and secondary outcomes analyzed for 72 infants (N=35 conventional, N=37 study). For study vs conventional groups, respectively: a) 33%(95% CI, 19%-49%) vs 44%(95% CI, 28%-62%), p=0.28 achieved primary outcome success, and b) secondary outcomes did not significantly differ (p>0.05).

**CONCLUSIONS:** Feeding strategy modifications concurrent with acid suppression are not superior to PPI alone in improving GERD symptoms or discharge feeding, short-term and long-term outcomes.

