**Table 1. Baseline Demographic and Clinical Characteristics of Enrolled Participants**

Variable	Overall Subjects (N = 76)	Conventional Group (N = 36)	Study Group (N = 40)
At Birth			
Gender, Female – n (%)	37 (49)	18 (50)	19 (48)
Race – n (%)			
African American	11 (15)	3 (8)	8 (20)
Asian	1 (1)	0 (0)	1 (3)
Other	6 (8)	2 (6)	4 (10)
Unknown	1 (1)	1 (3)	0 (0)
White	57 (75)	30 (83)	27 (68)
Ethnicity – n (%)			
Hispanic or Latino	2 (3)	2 (6)	0 (0)
Non Hispanic or Latino	71 (93)	32 (89)	39 (98)
Unknown	3 (4)	2 (6)	1 (3)
Gestational Age (GA) – wks	29.3 [27 - 32.9]	29.3 [28 - 32.2]	29.2 [27 - 33.1]
Preterm birth – n (%)	68 (90)	34 (94)	34 (85)
Birth Weight – kg	1.23 [0.9 - 1.9]	1.2 [0.9 - 1.9]	1.3 [0.9 - 2.1]
Size for Gestational Age – n (%)			
Small (< 10th %)	9 (12)	5 (14)	4 (10)
Average (10th - 90th %)	58 (76)	26 (72)	32 (80)
Large (> 90th %)	9 (12)	5 (14)	4 (10)
Cesarean Delivery – n (%)	50 (66)	22 (61)	28 (70)
At Inception			
Postmenstrual age – wks	41.1 (2.5)	41.3 (2.2)	40.9 (2.7)
Chronologic age – wks	10.9 (4.3)	11.1 (4.5)	10.7 (4.3)
Weight – kg	3.5 (0.8)	3.5 (0.8)	3.5 (0.8)
O 2 Requirement at 36 wks PMA – n (%)	36 (47)	17 (47)	19 (48)
O 2 Requirement at 28 days age – n (%)	46 (61)	21 (58)	25 (63)
Feeding Method – n (%)			
Gavage	2 (3)	0 (0)	2 (5)
Transitional	37 (49)	18 (50)	19 (48)
Oral	37 (49)	18 (50)	19 (48)
Nasal Cannula Oxygen – n (%)	23 (30)	11 (31)	12 (30)
Total Intake Volume – mL/kg/day	150 [149 - 154]	150 [148 - 152]	150 [150 - 157]
Total Oral Intake Volume – mL/kg/day	112 [45 - 150]	112 [57 - 150]	112 [22 - 148]
Acid Reflux Index (ARI) – %	9.3 [6.0 - 17.1]	10 [6.0 - 16.7]	9.1 [5.0 - 17.6]
ARI Category – n (%)			
Indeterminate (ARI 3 - 7%)	26 (34)	12 (33)	14 (35)
Abnormal (ARI > 7%)	50 (66)	24 (67)	26 (65)

Data presented as n (%), Median [IQR], or Mean (SD).

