  - Every patient who had been randomized will be included in the analysis. If a patient drops off before end of study and no symptom score has been measured, we will treat the patient as a failure. Beside the intention to treat analysis, we will also perform the analysis with only those patients that complete the study. Linear mixed models will be used to study the associations between the primary endpoints for Aim 1 (symptom scores) and treatment, and trend across time. The interaction term “group x time” will be included in the model to study whether the two treatment groups have different “behavior” across time. Confounder variables, such as medications, feeding position or volume, will be included in the models. Logistic regression models will be used to assess success of the treatment vs. standard of care. Also, potential confounders (e.g. feeding method: oral vs. tube) will be included and studied in these models. Holm's method will be used to adjust for multiple comparisons. All the secondary variables listed above, will be analyzed using either linear mixed models or logistic regression models. Model goodness of fit tests and residual analyses will be performed to assess the models. Interaction terms and potential confounder variables will be included.
  - The proposed projects will focus on esophageal provoking stimuli in designing multi-faceted innovative therapies, that will be studied in a prospective single center randomized blinded controlled trial. The pH- Impedance data with associated symptom indices will be analyzed. This trial will advance our knowledge of GER and GERD in infants. These studies will likely mandate the development of infant-specific diagnostic and treatment paradigms to manage not only GERD but also other diseases where GERD is a co-morbidity.

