- Overall Study Endpoints: Primary clinical outcome occurs at time 2 study or at discharge if time 2 study not completed. Secondary study outcomes occur at time 2 studies. Secondary clinical outcome measures (growth characteristics, development and long term feeding outcomes) will be collected up to 24 months.
- Methods to overcome potential confounders: Data will be collected from EPIC documentation, feeding diaries, parent interviews and follow up appointments. While inpatient, these are documented regularly. After discharge, we will be dependent on parents to provide the data.
- Removal and management of subject(s) from protocol: The investigator and/or the parent(s) have the right to withdraw from study at any time and opt for the standard of care. Parent(s) that withdraw their infants from the study therapy will be encouraged to continue to remain in the study for all follow up evaluations. Those who choose completely withdrawal from the study will be encouraged to follow the standard of care; wherein, response failures are followed for secondary outcomes until 18 months.
- Secondary Outcome Measures: (up to 24 months, for Bayleys developmental score) Secondary outcome measures (growth characteristics, development and long term feeding outcomes) will be collected up to 12 months.

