## **13.0 Withdrawal of Subjects\***

- If a subject develops any condition outlined in the exclusion criteria (i.e. surgical or neurological conditions) they will be withdrawn
- Subjects will be withdrawn if there are any safety concerns
- Parents can choose to withdraw their infant at any time during the study period, but some data collection will continue.

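### Secondary outcomes are analysed on 72 of the 76 randomised infants, although the plan's intention-to-treat section includes all randomised infants and makes the completer analysis an addition

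*Combined protocol and SAP*

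**What the plan says.** Protocol section 3.3, under the intention-to-treat heading, sets the population: "Every patient who had been randomized will be included in the analysis". A randomised infant who drops out without a symptom score counts as a failure. An analysis of infants who finish the study is planned alongside this one. The same text assigns the secondary variables to mixed or logistic models and names no smaller population for them.

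The protocol also expects follow-up to outlast study treatment. Under section 6.1, parents who take an infant off study therapy "will be encouraged to continue to remain in the study for all follow up evaluations". Section 13.0 lets parents withdraw an infant at any time, "but some data collection will continue". Section 6.2 names the hospital electronic record as a source, and section 18.0 says that electronic records will be used for follow-up data.

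The report's Statistical Methods say "Seventy-six infants were randomly assigned till the end of funding for this study", and Table 1 and the primary analysis use all of them (36 conventional, 40 study). For the rest, "Secondary outcome analysis was performed for 72 subjects"; the Abstract and Table 2 give the split as 35 and 37. The revision history records no change of analysis population.

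**The concern.** Leaving randomised infants out of a comparison gives up part of the protection of randomisation. Here the reduced set is the only analysis of the secondary outcomes, whereas the plan gives the completer analysis a supporting role. Length of stay, feeding method at discharge and oxygen at discharge are routine hospital facts that do not require an infant to stay on the assigned feeding strategy. They are therefore the outcomes for which an all-randomised analysis is most likely to be feasible.

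The arms are small, so each infant carries 2.5 to 2.8 percentage points of a proportion (1/40 and 1/36). The report presents its finding of no secondary differences as support for the statement that restrictive feeding has no impact. A reader should be able to see how far those differences could move.

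**Working it through.** **Inputs.** Randomised: 36 conventional, 40 study (Table 1). Analysed for secondary outcomes: 35 and 37 (Table 2). Counts from Table 2, conventional then study:
- full oral feeding at discharge: 29/35 and 25/37
- full oral feeding at Time 2: 27/35 and 24/37
- oxygen at discharge: 9/35 and 7/37

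**Omissions.** 36 - 35 = 1 conventional (1/36 = 2.8%); 40 - 37 = 3 study (3/40 = 7.5%). Fisher's exact test of 1/36 against 3/40 gives p=0.62.

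**Reproducing the report.** Oxygen, uncorrected chi-square: 0.488 (stated 0.49). Feeding over three categories, exact test: 0.265 at Time 2 (stated 0.26) and 0.319 at discharge (stated 0.32). Primary outcome, 16/36 against 13/40: 0.284 (stated 0.28). The published figures reproduce.

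**Who the four were.** Table 1 gives feeding at inception for all 76, and Table 3 for those analysed (18 + 17 = 35 and 20 + 17 = 37). Table 3 also returns the Time 2 oral-feeding totals of Table 2 (11 + 16 = 27 and 7 + 17 = 24), so it appears to describe the same 72.

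| Group at inception | Table 1 | Table 3 | Omitted |
|---|---|---|---|
| Conventional, oral | 18 | 17 | 1 |
| Conventional, any tube | 18 | 18 | 0 |
| Study, oral | 19 | 17 | 2 |
| Study, any tube | 2 + 19 = 21 | 20 | 1 |

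Three of the four were therefore fully orally fed at inception.

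**Bounds on all 76.** Let i (0 or 1) be the number with the outcome among the omitted conventional infants, and j (0 to 3) the number among the omitted study infants. With a and b the Table 2 counts for conventional and study:

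difference = (b + j)/40 - (a + i)/36

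The lowest value is at i=1, j=0; the highest is at i=0, j=3.

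| Outcome | On 72 | Lowest on 76 | Highest on 76 | Two-category chi-square p over all assignments |
|---|---|---|---|---|
| Oral feeding, discharge | 25/37 - 29/35 = -15.3 (p=0.13) | 25/40 - 30/36 = -20.8 | 28/40 - 29/36 = -10.6 | 0.043 to 0.29 |
| Oral feeding, Time 2 | 24/37 - 27/35 = -12.3 (p=0.25) | 24/40 - 28/36 = -17.8 | 27/40 - 27/36 = -7.5 | 0.096 to 0.47 |
| Oxygen, discharge | 7/37 - 9/35 = -6.8 (p=0.49) | 7/40 - 10/36 = -10.3 | 10/40 - 9/36 = 0.0 | 0.28 to 1.00 |

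Differences are in percentage points. The 0.043 for discharge feeding comes from the single most extreme of eight assignments; Fisher's test on that table gives 0.071. With the report's three feeding categories, the exact p runs from 0.078 to 0.66 at discharge and from 0.037 to 0.67 at Time 2. Both minima need the omitted conventional infant to be orally fed and all three omitted study infants to be fully tube-fed.

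**An assignment closer to the tables.** Suppose the three infants orally fed at inception stayed so and the tube-fed one did not reach full oral feeding.
- Discharge: 27/40 - 30/36 = 67.5% - 83.3% = -15.8 points, p=0.11 (-15.3 on 72).
- Time 2: 26/40 - 28/36 = 65.0% - 77.8% = -12.8 points, p=0.22 (-12.3 on 72).

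Under this assumption each difference moves by about half a point.

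**The case against.** The 72 is disclosed in the Abstract, the Methods and the Table 2 header. The report refers to Figure 1 for drop-outs, and that figure's content is not available here, so complete withdrawal of consent or a withdrawal required by section 13.0 cannot be excluded. Section 13.0 promises only some continued data collection, and the encouragement in section 6.1 applies to infants who leave study therapy, not to those who leave the study altogether. The plan's failure rule is tied to a missing symptom score; it gives no rule for missing length of stay, growth or oxygen. Other losses are larger: I-GERQ-R response is reported on 65, feeding at 6 months on 50 and at 1 year on 44. All of this stands. It limits what can be recovered, but it does not supply a reason for departing from the stated population or for omitting a sensitivity analysis.

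A reader might infer that the omission removed the infants who did worst, mainly from the study arm. The documents do not support that. Three against one is compatible with chance, and three of the four were already orally fed. Among the analysed infants who began on oral feeds, 16 of 17 and 17 of 17 kept them (33 of 34). Counting all four as not orally fed at discharge gives 25/40 against 29/36 (62.5% vs 80.6%, -18.1 points, p=0.08), but that needs those three to have lost oral feeding. It belongs inside the bounds and should not be taken as the expected result.

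**Conclusion.** The point holds as a departure from the plan's own population rule with a modest numerical effect. Secondary outcomes rest on 72 of 76 randomised infants, with no reason given in the text, and the planned all-randomised analysis of them is not shown. Whether the loss is informative is unknown.

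No assignment of the four makes oral feeding look better in the study arm, and only the most extreme assignments against that arm bring any p-value below 0.05. Oxygen never approaches significance. The primary analysis already includes all 76, so the conclusion of non-superiority stands. A reader might infer that the reduced set hides a harmful effect on feeding; values reached only at the edge of the bounds do not establish one.

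Two assumptions matter: that Table 3 describes the same 72 infants, which its totals support, and that some discharge data for the four exist, which is an inference from the protocol's follow-up provisions.

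**What to change.** Report length of stay, feeding method at discharge and oxygen at discharge on all 76 infants where the hospital record permits. Where a value cannot be obtained, give best-case and worst-case bounds for the binary outcomes, as tabulated above. State for each of the four infants why the data were left out, and label the 72-infant analysis as a completer analysis presented beside the all-randomised one.

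The cost is a check of four charts and a re-run of the tables, with slightly wider uncertainty around the secondary results.

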## STUDY OUTCOMES

### Primary and Secondary Clinical Outcomes

The clinically meaningful primary and secondary outcomes did not differ significantly between groups (**Table 2**). I-GERQ-R scores for study and conventional groups are shown (**Fig 2**). At inception: positive I-GERQ-R was 19/35 (54%) in the conventional group vs 24/37 (65%) in the study group,  $p=0.36$ . At Time-2: positive I-GERQ-R prevalence was 9/31 (29%) in the conventional group vs 13/34 (38%) in the study group,  $p=0.43$ . In the study group vs conventional group, respectively: a) primary outcome achieved in 33% (95% CI, 19% - 49%) vs 44% (95% CI, 28% - 62%) ( $p=0.28$ ), b) secondary outcomes: independent oral feeding in 65% (95% CI, 48% - 80%) vs 77% (95% CI, 60% - 90%),  $p=0.26$ ,  $\geq 6$ -point I-GERQ-R decrease in 38% (95% CI, 22% - 56%) vs 35% (95% CI, 19% - 55%),  $p=0.82$ , length of stay was 98 [81-132] days vs 108 [83-125] days,  $p=0.89$ , and oxygen requirement at discharge in 19% (95% CI, 8% - 35%) vs 26% (95% CI, 13% - 43%),  $p=0.49$ . There were no significant differences in growth metrics (all  $p>0.05$ ) or developmental scores at 2 years (all  $p>0.05$ ). Feeding outcomes or I-GERQ-R scores did not significantly differ between conventional vs study groups based on feeding method at inception (**Table 3**). Individual I-GERQ-R questions relating to vomiting, regurgitation, and crying (i.e. frequency of emesis, volume of emesis, symptoms with emesis, and crying more than usual in the

past week) had no differences ( $P>0.05$ ) within the group or between the groups across maturation for these individual symptoms, except for symptoms with emesis (never: rarely: sometimes: often: always, %) was 16:16:42:19:6 for conventional group at Time-1 vs 18:18:29:0:35 for study group at Time-1,  $p < 0.01$ .

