**Table 2. Primary and Secondary Clinical Outcomes and Compliance Measures**

Primary Outcome (intent-to-treat analysis)	Overall (N = 76)	Conventional (N = 36)	Study (N = 40)	P-value
A priori clinical outcome Success, n (%)	29 (38)	16 (44)	13 (33)	0.28
Secondary Outcomes	Overall (N = 72)	Conventional (N = 35)	Study (N = 37)	P-value
I-GERQ-R decrease by 6 – n (%)	24/65 (37)	11/31 (35)	13/34 (38)	0.82
Feeding Outcome at Time 2 – n (%)				0.26
PO	51 (71)	27 (77)	24 (65)	
Transition (PO + Tube)	18 (25)	8 (23)	10 (27)	
Tube	3 (4)	0 (0)	3 (8)	
Length of hospital stay – days	108 [82 - 128]	108 [83 - 125]	98 [81 - 132]	0.89
Hospital stay Inception to Discharge – days	25 [11 - 45]	23 [3 - 39]	27 [16 - 47]	0.26
Weight Growth Velocity (GV) – g/day	27.1 (9.4)	26.5 (7.2)	27.6 (11.1)	0.64
Length GV – cm/day*	0.1 (0.1)	0.1 (0.1)	0.1 (0.1)	0.88
Head Circumference GV – cm/day*	0.1 [0.0 - 0.1]	0.1 [0.0 - 0.1]	0.1 [0.0 - 0.1]	0.87
Feeding Method at Discharge – n (%)				0.32
PO	54 (75)	29 (83)	25 (68)	
Transition (PO + Tube)	14 (19)	5 (14)	9 (24)	
Tube	4 (6)	1 (3)	3 (8)	
Oxygen Requirement at discharge – n (%)	16 (22)	9 (26)	7 (19)	0.49
Compliance to Feeding Methods				
Total Fluid Volume (TFV)				
TFV at Inception- #	N/A	150 [147, 152]	150 [149, 156]	0.8
TFV at Time 2- #	N/A	143 [134, 148]*	133 [126, 137]*	<0.001
# days TFV ≤ 140 / kg / day	N/A	10 [2, 26]	22 [11, 31]	0.005
TFV compliance (TFV <140/kg/d for >75% of time)	N/A	9 (26)	27 (73)	<0.001
Position				
Feeding Position, RSL, %	N/A	5 [1, 17]	78 [12, 94]	<0.001
Feeding in RSL >75% of the time, %	N/A	0 (0)	21 (57)	<0.001
Supine Position Post-Prandial, %	N/A	50 [40, 66]	87 [74, 96]	<0.001
Supine Position Post-prandial >75% of the time, %	N/A	7/34 (21)	27/36 (75)	<0.001
Feeding Duration				
% time feed duration >30 min, %	N/A	4 [0, 37]	15 [0, 69]	0.15
Feeding Duration at Inception, min	N/A	23 [17, 41]	30 [19, 34]	0.64
Feeding Duration at Time 2, min	N/A	23 [18, 28]	26 [20, 30]	0.15
Long-term Follow-up†				
Feeding Method at 6 months – n (%)				0.65
PO	36/50 (72)	21/27 (78)	15/23 (65)	
Transition (PO + Tube)	10/50 (20)	4/27 (15)	6/23 (26)	
Tube	4/50 (8)	2/27 (7)	2/23 (9)	
Feeding Method at 1 year – n (%)				0.11
PO	37/44 (84)	20/22 (91)	17/22 (77)	
Transition (PO + Tube)	4/44 (9)	0/22 (0)	4/22 (18)	
Tube	3/44 (7)	2/22 (9)	1/22 (5)	
CCABSID-III				
Cognitive Score <80 – n (%)	9/44 (21)	5/23 (22)	4/21 (19)	1.00
Cognitive Score – #	95 [90 - 105]	100 [90 - 105]	90 [90 - 100]	0.11

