**Table 3. Feeding and I-GERQ-R Outcomes by Feeding Method at Inception**

Outcome	Conventional	Study	P-value
Among those Tube fed at Inception			
Achieved exclusive oral feeding	N = 18	N = 20	
Achieved I-GERQ-R decrease $\geq 6$	11 (61)	7 (35)	0.11
Achieved PO or I-GERQ-R decrease $\geq 6$	7/17 (41)	8 (40)	0.94
Achieved exclusive oral feeding + I-GERQ-R decrease $\geq 6$	14 (78)	13 (65)	0.39
	4/17 (24)	2 (10)	0.38
Among those PO fed at Inception	N = 17	N = 17	
Maintained PO	16 (94)	17 (100)	1.0
Achieved I-GERQ-R decrease $\geq 6$	4/14 (29)	5/14 (36)	1.0
Maintained PO or I-GERQ-R decrease $\geq 6$	16 (94)	17 (100)	1.0
Maintained PO + I-GERQ-R decrease $\geq 6$	4/14 (29)	5/14 (36)	1.0

[figure not shown]
Data presented as n (%).

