- Sample Size Determination:
  - From the more recent preliminary data analysis, 83.3% (20/24, 95% CI: 62.6%-95.2%) of patients had success based on symptoms and feeding methods in the innovative strategy group, while only 35% (7/20, 95% CI: 15.4%-59.2%) had success in the standard therapy group. In order to provide greater assurance than afforded by comparing to historical control of the standard therapy, a total of evaluable 100 patients will be randomized into the innovative feeding strategy or standard therapy group. The chi- square test yields 80% power to detect 27% or higher increase in proportion of success while maintaining an overall one-sided  $\alpha$  level of 0.025. This conservative power calculation is supported by the preliminary data and assumes the proportion of success for the standard therapy is around 40% and a group-sequential design with O’Brien-Fleming error spending function.
- Interim Analysis:

- One interim futility analysis will be undertaken at about 50% information prior to the final analysis at 100% information, corresponding to 50 and 100 evaluable patients, respectively. The boundary is determined using Lan-DeMets spending functions to simulate O'Brien-Fleming boundaries with an overall one-sided  $\alpha$  level of 0.025. Using the target proportion of success, the boundary at the futility analysis expressed as a p-value is 0.297. We plan to enroll 120 patients to allow for 20% of attrition.
- Intention to treat analysis:

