## 4.0 Study Endpoints

- Primary Outcome
  - **Clinical outcome of feeding success for those infants transitioning to oral feeds at inception.**
    - The primary endpoint is the feeding success defined as achieving full oral feeds (defined as no need for tube feeds to maintain hydration and nutrition) and/or a  $>/=$  6-point decrease from baseline I-GERQ-R. The time frame is up to 5 weeks after enrollment.
  - **Clinical outcome of feeding success for those infants on full oral feeds at inception.**
    - The primary endpoint is the feeding success defined as maintaining full oral feeds and a  $>/=$  6-point decrease from baseline I-GERQ-R. The time frame is up to 5 weeks after enrollment.
- Secondary Outcomes
  - Clinical Outcomes
    - Length of hospital stay
    - Growth outcomes during the study period and up to 1 year
    - Independent feeding skills over time up to 1 year
    - Respiratory support during the study period and at discharge
    - Developmental outcomes with Bayley's scores at 2 years
    - Individual differences in I-GERQ-R questionnaire
  - Motility Outcomes
    - Mechanisms of aerodigestive clearance and esophageal provocation are evaluated based on esophageal motility studies at inception and after 5 weeks.
  - pH Impedance outcomes
    - 24-hour pH impedance results at inception of study and then 5 weeks later after treatment completed

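### Primary success counts in Tables 2 and 3 do not agree, and the interim futility statement gives no direction, side or counts and is hard to square with the final result

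*Combined protocol and SAP*

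**What the plan says.** **Endpoint.** Section 4.0 of the protocol and Outcome Measures in the report use one definition in two parts. An infant still moving to oral feeds succeeds by reaching full oral feeds or by a drop of 6 or more points in I-GERQ-R. For an infant already on full oral feeds, "The primary endpoint is the feeding success defined as maintaining full oral feeds and a" drop of 6 or more points; both are needed.

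**Result.** Table 2, the abstract and the outcomes text give 13/40 (33%) study and 16/36 (44%) conventional, p=0.28. Table 3 gives the components by feeding method at inception, including a row "Maintained PO + I-GERQ-R decrease" of 6 or more points for infants already on oral feeds.

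**Missing scores.** Statistical Methods counts a dropout without an evaluable symptom score as a failure.

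**Interim.** Protocol section 3.3 plans one futility look at 50 of 100 evaluable infants, with overall one-sided alpha 0.025: "Using the target proportion of success, the boundary at the futility analysis expressed as a p-value is 0.297". The report states "Futility boundary was not reached at interim analysis of 50 patients" (p=0.1, below 0.297) "and accrual was continued with DSMB approval". It does not say which arm was ahead, whether p was one- or two-sided, or how many successes each arm had. The limitations paragraph adds that on 72 infants the trial would have stopped for futility.

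**The concern.** Two reported facts that should follow from the data do not fit together.

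First, Table 3 contains every cell needed to rebuild the primary endpoint, and the rebuilt counts differ from Table 2 in both arms. The published size of the difference (-12 points or -5 points) depends on which table is used.

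Second, a futility rule of this kind has a direction. A small p avoids stopping only if it is a one-sided p in favour of the study arm. The final result has the study arm behind. If the interim p was instead an undirected chi-square p with the study arm behind, the comparison with 0.297 was made on the wrong scale and the boundary had been crossed. Up to 26 of the 76 infants were randomised after that look.

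**Working it through.** **1. Rebuilding the primary counts from Table 3**

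In the extracted text, the Table 3 labels for tube-fed infants sit one line away from their values. Sums confirm the reading used here:

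| Check | Conventional | Study | Table 2 |
|---|---|---|---|
| Oral feeding at Time 2 | 11+16=27 | 7+17=24 | 27 and 24 |
| Drop of 6 or more points | 7+4=11 of 31 | 8+5=13 of 34 | 11/31 and 13/34 |
| Tube-fed, either component | 11+7-4=14 | 7+8-2=13 | not given |

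Scored by the section 4.0 definition:

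- Conventional: 14 (tube-fed, either) + 4 (orally fed, both) = 18.
- Study: 13 + 5 = 18.

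Effect of the missing-score rule:

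- All 20 tube-fed study infants have a score, and the 5 orally fed successes have one by definition, so study stays at 18.
- One of the 18 tube-fed conventional infants has no score (17 scored), so conventional is 17 or 18.
- Table 3 covers 72 infants (35 and 37). The other four (1 conventional, 3 study) could only add successes.

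Other combinations also miss the reported 16 conventional and 13 study. In that order: oral feeding alone if tube-fed plus both components if orally fed, 15 and 12; score drop alone, 11 and 13; both components in all, 8 and 7; either component in all, 30 and 30.

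Pearson chi-square without continuity correction, difference as study minus conventional:

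- Table 2, 13/40 vs 16/36: Z = -1.07, two-sided p = 0.284, which is the reported 0.28. Difference -11.9 points (95% CI -33.7 to 9.8).
- Table 3, 18/40 vs 18/36: Z = -0.44, two-sided p = 0.663. Difference -5.0 points (-27.5 to 17.5).

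**2. Reproducing the 0.297 boundary**

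Inputs (section 3.3): one-sided alpha 0.025, power 80% (beta 0.20), one look at information t = 0.5, Lan-DeMets O'Brien-Fleming-type spending.

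- Beta spent: 2[1 - Φ(1.2816/√0.5)] = 2[1 - Φ(1.812)] = 0.0699.
- Drift for 80% power with a binding futility bound: 2.843.
- Boundary: Z = Φ⁻¹(0.0699) + 2.843 × √0.5 = -1.476 + 2.010 = 0.534.
- One-sided p = 1 - Φ(0.534) = 0.2966, which rounds to 0.297.

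So 0.297 is a one-sided superiority p. Accrual continues only if Z (study minus conventional) exceeds about 0.53. At 25 per arm, 10 vs 8 successes passes (Z = 0.59) and 9 vs 8 does not (Z = 0.30).

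**3. What the final totals imply about the first 50**

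If 25 per arm entered first, the Table 2 totals give expected successes of 13×25/40 = 8.1 and 16×25/36 = 11.1; 8 vs 11 gives Z = -0.87. All interim tables were then enumerated with hypergeometric weights (random entry order), for study-arm sizes 21 to 30 of 50. The reported p of 0.1 was read as 0.05 to 0.15.

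| Event at 50 infants | Table 2 totals (40/36) | Table 3 totals (40/36) |
|---|---|---|
| Z above 0.53 (not reached) | 0.5% to 1.2% | 6% to 9% |
| Study ahead, p near 0.1 (one- or two-sided) | 0.03% to 0.12% | 0.9% to 1.5% |
| Study behind, two-sided p near 0.1 | 8% to 16% | 1.6% to 3.7% |

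With the same successes placed on 37/35, the first row becomes 0.7% to 1.5% (Table 2) and 10% to 13% (Table 3).

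Two examples at 25 per arm with Table 2 totals:

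- Study ahead, 11/25 vs 7/25: Z = 1.18, one-sided p = 0.12. The remaining 26 infants must then be 2/15 (13%) vs 9/11 (82%).
- Study behind, 7/25 vs 13/25: two-sided p = 0.083, leaving 6/15 (40%) vs 3/11 (27%). Here the one-sided p is 0.96, far past 0.297.

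**The case against.** **The interim statement is not disproved.** Arm counts, direction and side at 50 infants are unpublished, and tables exist that satisfy every printed figure. The probabilities assume random entry order, and an arm-by-time reversal cannot be excluded. The look was planned on evaluable infants, while the final 76 include dropouts scored as failures, so interim scoring may have differed. All of this stands. A reader might infer that the boundary was certainly crossed, or that the DSMB knowingly continued past it. The documents support neither.

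**A minimum size for the later reversal.** It is tempting to say that conventional must have led by at least 42 points in the last 26 infants. That holds only for interim splits from 22/28 to 28/22. The minimum is 18 points at 29/21 and zero at 30/20, and no split is reported. The probabilities stay small at those splits; the point bound does not survive.

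**One statement wrong, the other right.** A reader might conclude that the interim statement is wrong if Table 2 is right, and sound if Table 3 is right. That does not follow. On Table 3 totals the chance of passing the boundary is still only about 6% to 9%, so both statements could be wrong.

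**Assessment time.** Outcome Measures scores the endpoint at 5 weeks or at discharge if earlier; protocol section 6.1 uses the Time 2 study, or discharge if that was not done. Table 3 ties to Time 2 feeding. Tables 2 and 3 might therefore use different times. Oral feeding at discharge is higher (29 and 25, against 27 and 24), so feeding totals alone do not explain fewer successes, but I-GERQ-R at discharge is not reported. This remains open, and for that reason 45% vs 50% should not be presented as the true result.

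**Conclusion.** The concern holds in two parts of different strength.

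The discrepancy in the primary counts is a matter of arithmetic. By the stated definition Table 3 gives 18 study and 18 conventional (17 at the lowest); Table 2 gives 13 and 16. Nothing in the documents reconciles them or shows which is right. The difference moves from -12 to -5 points and p from 0.28 to 0.66. The study arm is not superior on either set, so the trial's conclusion is unchanged. No superiority was claimed, so false-positive error is not at issue.

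The interim part is strong implausibility. Given a one-sided boundary and the Table 2 totals, passing it at 50 infants had a chance of about 1%. An undirected p near 0.1 with the study arm behind is much the more likely reading of those totals, but the documents do not confirm it. On Table 3 totals the direction of p=0.1 is not settled. These figures rest on random entry order, the same scoring at interim and final, and p=0.1 being a one-decimal rounding. The later statement that the trial would stop on 72 infants agrees with the final counts. The success rates were "compared using chi-square test between the conventional and study groups (primary outcomes"), and the final p of 0.28 is two-sided, so a two-sided p may also have been used at the interim; that is inference.

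**What to change.** 1. Rescore the primary endpoint from existing data by the section 4.0 definition. State the assessment time and how missing scores were handled, and publish one reconciled set of counts in Table 2, Table 3 and the abstract.
2. Recompute the signed interim Z (study minus conventional) from the first 50 evaluable infants. Report it in Statistical Methods with successes and denominators by arm and the side of the p-value, next to the boundary (Z 0.53, one-sided p 0.297).
3. If that Z was at or below 0.53, correct the sentence to say that the boundary was crossed and accrual continued.

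The cost is one rerun of existing data and possibly a published correction. No new data are needed.
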